6. SAMPLE SIZE CONSIDERATIONS

The sample size is a convenience sample of 200 subjects (100 subjects per treatment group).

7. DATA QUALITY ASSURANCE

Data quality assurance will start with training of clinical investigative staff on data collection and assessment procedures including a Manual of Operations that describes what data to collect and procedures for completion of eCRFs. Completed eCRFs will be reviewed by [REDACTED] [REDACTED] clinical monitors on a regular basis throughout the trial by comparison against the source documents.

All study data will come from the eCRFs and no other source data. eCRFs for this study were created using an electronic data management system (EDMS) [REDACTED]. eCRFs were created using an established data dictionary for each variable including the field name, field type, field attributes, and coding for variables. Range checks, alpha-numeric requirements, and null/not null parameters were programmed as applicable. Data entered into the EDMS system will be reviewed by [REDACTED] clinical monitors and data managers. If

incomplete or inaccurate data are found, the data will be queried in the system for site staff to address. The site will resolve data inconsistencies and errors using the EDMS with full audit trail of corrections being maintained within the system. Corrections and changes to the data will be reviewed by [REDACTED] clinical monitors and data managers.

Additional edit checks will be written to detect anomalies in the database. These checks will address inconsistencies (within visits, across visits), invalid/unusual values, missing values, and protocol violations. Edit checking will be validated on test data or actual clinical trial data. In addition to programmed edit checks, quality control examination of data will also be performed on reviews of data listings.

8. STATISTICAL CONSIDERATIONS

8.1. General Considerations

For descriptive purposes, dichotomous variables will be presented as number of observations and percentages; continuous variables will be given as means, standard deviations (SD), median, and range. All data will be presented in listings.

8.2. Participant Accountability and Protocol Deviations

A summary will be prepared to show the reason for early termination. Protocol deviations will be presented as summaries by type of deviation.

8.3. Demographics and Surgical Characteristics

Summaries of the characteristics of the subjects in each of the study groups at baseline will be prepared for the full and per protocol analysis sets. Demographic characteristics (e.g., age, gender, race, and ethnicity), antibiotic use prior to surgery, wound classification, and surgery category and type will be presented in tables and subject listings.

8.4. Efficacy Analysis

8.4.1. SSI Rates

The number and percentage of patients who were diagnosed with an SSI at any time post surgery will be presented to the full analysis set and the PP analysis set. The rates by type of SSI, superficial incisional, deep incisional, and organ space will also be summarized. A listing will be provided by patient that includes these endpoints as well as the medical findings that contributed to each diagnosis.

8.4.2. Antibiotic Use

The number and percentage of patients who were prescribed prophylactic antibiotics and antibiotics to treat an infection will be summarized by treatment group for each analysis set.

8.4.3. Preoperative Surgical Skin Prep Instructions

The number of patients prepped following the [REDACTED] standard pre-operative skin prep procedures using a topical antiseptic agent will be summarized.

8.5. Handling of Missing Data

Missing Data will not be imputed.

8.5.1. Missing Data within Dates

Missing dates are handled as follows:

- Missing day: The first day of the month will be used.
- Missing Month: The first month of the year will be used.

Completely missing dates will remain missing, with no imputation applied. Consequently, time to onset and duration of such events will be missing.

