10.1.3. Methods/Timing for Assessing, Recording, and Analyzing Safety Endpoints

AEs will be assessed starting after the first administration of investigational product until the final follow-up at Day 30. General symptoms will be collected via an open ended question: How have you been feeling since the last time we spoke? Elicited AEs will be assessed as described in section [10.1.4](#).

AEs will be documented in the medical/source records, and recorded on the eCRF using accepted medical terms and/or the diagnoses that accurately characterize the event. When a diagnosis is known, the AE term recorded on the eCRF will be the diagnosis rather than a constellation of symptoms. The investigator will assess all AEs for seriousness, relationship to investigational product, and severity. When an event has not resolved by study closure, it will be documented on the AE CRF as “ongoing”.

All AEs, including clinically significant abnormal findings on laboratory evaluations, regardless of severity, will be followed by study physicians until satisfactory resolution (the event either resolved or stabilized and is not expected to resolve in the near term). At the follow-up telephone contact, AEs will be recorded and followed to resolution only if they are serious, or if the study physician assesses them to be clinically significant.

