10.1.7. Reporting Serious Adverse Events

10.1.7.1. 24-hour Reporting Requirements (Initial Report)

Any SAE, including death due to any cause, which occurs to any patient from the time of signing consent through the final follow-up telephone call whether or not related to the investigational product, must be reported **within 24 hours** of knowledge of the event by completing the AE/SAE eCRF. This will trigger an automatic notification of the SAE via an email communication to Zurex and [REDACTED]. [REDACTED] will notify the Medical Monitor upon receipt of the notification and coordinate communications with the Medical Monitor.

10.1.7.2. 3-Day Supporting Documentation Requirements

Written documentation for all SAEs must be received by Zurex and [REDACTED] within 3 business days of reporting the event. Required eCRFs that must be completed include the following:

- AE/SAE eCRF (revised if additional information is available)

In addition, scanned copies of the following may be requested to be uploaded to the data management system.

- Copies of medical records/source documents pertinent to the event (laboratory reports, ECG tracings, medical chart notes, etc.). These should be identified only by Patient number and not include any patient identification information prohibited by Health Insurance Portability Accountability Act (HIPAA).
- Any other relevant information necessary to support the investigator's judgment regarding the SAE's relatedness severity to the investigational product OR by request of the Medical Monitor/Alternate.

These paper documents may be submitted by facsimile, as email attachments, or by attaching them to the patient's eCRF casebook in the electronic data management system (EDMS).

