8.6. Safety Analysis

8.6.1. Adverse Events

AEs will be coded using the most recent version of the MedDRA and will be grouped by SOC and preferred terms designation. The severity, frequency, and relationship of AEs to investigational product will be presented by SOC and preferred term groupings. Elicited AEs will be separately tabulated by treatment group. Listings of each individual AE including start date, stop date, severity, relationship, outcome, and duration will be provided. Each AE (based on preferred terminology) will be counted once only for a given study subject. If the same AE occurred on multiple occasions, the highest severity will be assumed. Thus, study subjects are not counted multiple times in a given numerator in the calculation of frequencies for a specific AE.

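### The partial-date rule in SAP 8.5.1 has no floor at surgery and no separate stop-date rule, so it can date post-operative events before surgery and give negative durations

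*SAP*

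**What the plan says.** SAP 8.5.1 gives one rule for all partial dates. For the day: "Missing day: The first day of the month will be used". For the month: "Missing Month: The first month of the year will be used". Start and stop dates are not distinguished, and there is no lower or upper bound. Only a wholly missing date stays missing, and for that case the section adds: "Consequently, time to onset and duration of such events will be missing". Time to onset and duration are therefore the quantities the SAP derives from these dates.

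SAP 8.6.1 puts the dates into output: "Listings of each individual AE including start date, stop date, severity, relationship, outcome, and duration will be provided".

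The parent section, SAP 8.5, says: "Missing Data will not be imputed". It does not mention the exception that follows in 8.5.1.

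Protocol 10.1.3 starts adverse event assessment after the product is first applied and ends it at Day 30, but says that events "will be followed by study physicians until satisfactory resolution". Protocol 10.1.7.1 sets a wider window for serious events: "from the time of signing consent through the final follow-up telephone call". Protocol 7.9 allows up to 21 days between consent and surgery.

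**The concern.** In a trial with a month of follow-up, the first of the month is a poor stand-in for an unknown day. If the event falls in the same calendar month as surgery, the imputed onset precedes surgery unless surgery was itself on the 1st. A stop date moved back to the 1st can likewise land before a known start date. Both results come from following the SAP exactly.

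The errors would appear in time to onset and in the start dates, stop dates and durations of the adverse event listings. Two features of this trial add to the problem:

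- Relationship to product is judged partly on timing (Protocol 10.1.5). A listed onset before application would seem to contradict a rating of possible or stronger, and skin and allergic reactions attributed to each product are a primary safety objective.
- Serious events are collected from consent. A post-operative serious event moved to before surgery can therefore pass for a genuine pre-treatment event rather than stand out as a date error.

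A weaker possibility concerns antibiotics. If they are sorted into SAP Tables 4-5 (before surgery) or 12-13 (during and after) by imputed date, some could be misplaced. The SAP does not say how they are sorted.

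**Working it through.** The documents give no figure to reproduce, so the rule was applied to enumerated dates.

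**Inputs from the documents.** Day set to 1 and month set to January (SAP 8.5.1); follow-up to Day 30 (Protocol 10.1.3); consent up to 21 days before surgery (Protocol 7.9).

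**Assumptions.** 365 surgery dates, 1 July 2021 to 30 June 2022, equally likely; onset k days after surgery, k = 1 to 29. Calendar year 2022 gives the same shares. Duration is stop minus start.

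**Worked example.** Surgery 20 September 2021, onset recorded as September 2021:

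- Imputed onset is 1 September: 1 − 20 = −19 days from surgery.
- Onset known as 22 September and stop recorded as September: 1 − 22 = −21 days duration.
- Only the year of onset known: imputed onset is 1 January 2021, 262 days before surgery.

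**1. Onset day missing.** Share with first-of-month(surgery + k) < surgery:

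| Onset | Before surgery |
|---|---|
| k = 5 | 293/365 = 80.3% |
| k = 14 | 185/365 = 50.7% |
| k = 1 to 29 | 5,020/10,585 = 47.4% |

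Of the 5,020 cases, 4,641 (92%) fall 1 to 21 days before surgery, inside the longest consent-to-surgery period. If the day of surgery is counted as a possible onset day (k = 0 to 29), the share is 49%.

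**2. Onset month missing** (k = 1 to 29). Before surgery in 91.5% if the day is known, and in 95.6% if day and month are both missing.

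**3. Start complete, stop day missing.** Share with first-of-month(start + L) < start:

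| True duration L | Negative duration | Mean imputed duration |
|---|---|---|
| 3 days | 317/365 = 86.8% | −11.7 days |
| 7 days | 269/365 = 73.7% | −7.7 days |
| 14 days | 185/365 = 50.7% | −0.7 days |

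If both dates lack only the day, no duration is negative. With onset and stop both within the 30 days from surgery and all combinations weighted equally, the two dates then collapse to the same day in 68% of combinations.

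**4. Number of records.** The documents give no number of partial dates. For an assumed 2, 5 or 10 records lacking only the onset day, the expected number dated before surgery is 2 × 0.474 = 0.95, 5 × 0.474 = 2.4, or 10 × 0.474 = 4.7.

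**5. Effect of the fix.**

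- Onset = later of the surgery date and the first of the month: the share before surgery falls from 47.4% to 0, and the mean onset error from 14.7 to 9.9 days. 50.7% of imputed onsets then fall on the surgery date.
- Stop = last day of the month: no negative durations. A true 7-day event gets a mean of 21.7 days before any limit at the last follow-up information. The mean absolute error is 21.7 − 7 = 14.7 days, against 7 − (−7.7) = 14.7 days under the current rule.

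**The case against.** The strongest reply is that little depends on these dates. The study is descriptive (SAP 5). SSI is counted per patient, and adverse events once per patient and preferred term, with no visible date filter. No table title in SAP 10 names time to onset or duration. That stands, and it confines the problem to dates and derived intervals.

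Partial dates should also be rare. Sites are examined daily in hospital, telephone calls are scheduled, and SAP 7 plans edit checks: "These checks will address inconsistencies (within visits, across visits), invalid/unusual values, missing values, and protocol violations". Serious events, with 24-hour reporting and written documentation within 3 business days, are the records least likely to keep a partial date. This also stands: the percentages are conditional on a partial date and are not study-wide error rates. But checks and queries only reduce the number of such records; they put no bound on an imputed date. The validation in SAP 9 reviews tables for consistency with the plan, so it could confirm a faulty rule. A negative duration would be conspicuous, but a pre-surgery onset for a serious event might not be.

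The listing shells are redacted, so the listings may show raw dates or already flag imputed ones. That cannot be ruled out. Time to onset and duration would still need a workable rule.

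Finally, the last-day stop rule is no more accurate on average than the present one: it replaces underestimation with equal overestimation. That is correct before the last-information limit applies. Its gain is that impossible values disappear and the direction of error is known.

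**Conclusion.** The concern holds. SAP 8.5.1 is a stated rule that, applied as written, produces impossible values, and nothing else in either document repairs it. Among records lacking only the onset day, about 47% would be dated before surgery (80% for events at 5 days). Among 7-day events lacking only the stop day, about 74% would have a negative duration. These shares assume surgery dates spread evenly over the year; the first also assumes onsets spread evenly over days 1 to 29.

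The reach is limited. The number of partial dates is not stated and is probably small, and the missing-month case should be very rare in a 30-day follow-up. SSI and adverse event counts are not shown to change, and the antibiotic point depends on a sorting method the SAP does not give. The mismatch between 8.5 and 8.5.1 is editorial. The rule should be corrected before database lock because it is wrong as written and cheap to repair.

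**What to change.** Amend SAP 8.5.1 as follows:

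- **Start dates** (adverse events, SSI, post-operative antibiotics) with a missing day or month: use the later of the surgery/application date and the first day of the known period. Exempt records that show onset before surgery, such as a serious event between consent and surgery.
- **Stop dates** with a missing day or month: use the last day of the known period, but not before the start date and not after the last date of follow-up information for that event. Do not cap at Day 30, because Protocol 10.1.3 follows events to resolution.
- **Listings:** flag every imputed date and any duration derived from one.
- **SAP 8.5:** add that partial dates are an exception, with a reference to 8.5.1.

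The cost is a few sentences and a small programming change. Two side effects should be accepted openly: about half of imputed onsets (day missing, days 1 to 29) will fall on the surgery date, and a duration based on an imputed stop date becomes an upper bound when the start date is complete. The flag lets readers see both.

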8.6. Safety Analysis

8.6.1. Adverse Events

AEs will be coded using the most recent version of the MedDRA and will be grouped by SOC and preferred terms designation. The severity, frequency, and relationship of AEs to investigational product will be presented by SOC and preferred term groupings. Elicited AEs will be separately tabulated by treatment group. Listings of each individual AE including start date, stop date, severity, relationship, outcome, and duration will be provided. Each AE (based on preferred terminology) will be counted once only for a given study subject. If the same AE occurred on multiple occasions, the highest severity will be assumed. Thus, study subjects are not counted multiple times in a given numerator in the calculation of frequencies for a specific AE.

9. VALIDATION OF PROGRAMMING CODE

All SAS codes used to generate tables and listings will be validated and reviewed before being finalized. The validation process will be used to determine that the numbers are produced by a statistically valid method and that the execution of the computations is correct. Qualified personnel who have not previously been involved in the production of the original programming codes will perform the validation procedures. Methods of validation include independent programming and comparison to data listings. Tables will be reviewed for accuracy, consistency with this plan, consistency within tables, and consistency with corresponding output. Once validation is complete, a quality control reviewer will perform a final review of the documents for accuracy and consistency. Upon completion of validation and quality review procedures, all documentation will be collected and filed in the study documentation files [REDACTED].

10. TABLE, LISTING, AND FIGURE SHELLS

Table 1:	Subject Disposition - All Randomized Subjects.....	14
Table 2:	Demographic and Baseline Characteristics - mITT Subjects.....	15
Table 3:	Demographic and Baseline Characteristics - PP Subjects.....	16
Table 4:	Antibiotic Use Prior to Surgery – mITT Subjects	16
Table 5:	Antibiotic Use Prior to Surgery – PP Subjects.....	16
Table 6:	Surgery – mITT Subjects.....	17
Table 7:	Surgery – PP Subjects	17
Table 8:	Surgical Site Infection – mITT Subjects	18
Table 9:	Surgical Site Infection – PP Subjects	18
Table 10:	Type of SSI – SSI Subjects	18
Table 11:	Characteristics of SSI – SSI Subjects	18
Table 12:	Antibiotic Use During and Post Surgery – mITT Subjects	19
Table 13:	Antibiotic Use During and Post Surgery – PP Subjects	19
Table 14:	Overall Summary of Adverse Events – mITT Subjects	20
Table 15:	Number and Percentage of Subjects with Adverse Events - mITT Subjects.....	21
Table 16:	Summary of Subjects with Adverse Events by Severity and Relationship – [REDACTED]	22
Table 17:	Summary of Subjects with Adverse Events by Severity and Relationship – [REDACTED]	22
Table 18:	Number and Percentage of Subjects with Adverse Events by Maximum Severity - mITT Subjects	23
Table 19:	Number and Percentage of Subjects Adverse Events by Relatedness - mITT Subjects.....	23
Table 20:	Number and Percentage of Subjects with Elicited Adverse Events by Maximum Severity - mITT Subjects	24

Listings

[REDACTED]
[REDACTED]
[REDACTED]
[REDACTED]
[REDACTED]
